9.1.1. Treatment Schedules

P: SGT-53 treatment, IV, 3.6 mg DNA, twice/week for 3 weeks.

T: TMZ treatment, oral, 150 mg/m² daily, for 5 days in Cycle 1; 200 mg/m² daily for 5 days in Cycles 2 and 3.

With Optional Surgical Resection for Tumor Analysis

P: SGT-53 treatment, IV, 3.6 mg DNA, twice/week for 3 weeks.

T: TMZ treatment, oral, 150 mg/m² daily, for 5 days in Cycle 1; 200 mg/m² daily for 5 days in Cycles 2 and 3.

In case of holiday or other logistic issue, schedule will allow for SGT-53 treatments to be delivered on Monday and Thursday, or Tuesday and Friday of each week. If necessary, other schedules may be permitted with the approval of the Sponsor and PI.

9.2. Premedication

Pre-medication will follow emerging principles for liposomal agents, consisting of allergic prophylaxis and close monitoring for bronchospasm (i.e., grade 3 hypersensitivity reaction) and other signs of acute hypersensitivity (≥ grade 2 hypersensitivity). Specifically, for each infusion of SGT-53, patients will receive dexamethasone 8 mg i.v. 1 hour +/-5 minutes prior to dosing, and a combination of histamine H1 and H2 blockers (e.g. Benadryl 25 mg and Pepcid 20 mg, both i.v.) 30 minutes +/- 15 minutes and indocin 25 mg, or an equivalent NSAID, p.o. approximately 30 +/- 5 minutes prior to receiving SGT-53. All patients will also receive acetaminophen 650 mg p.o. just prior to SGT-53 administration as prophylaxis for pyretic reactions. Generic drugs may be used with prior approval from sponsor.

Premedications for temozolomide will be at investigator discretion, according to institutional practices. Antiemetic(s) suitable for controlling mild to moderate nausea and vomiting should be given prior to chemotherapy.

9.3. SGT-53 Infusion

Once the study drug is prepared, the investigational pharmacy will immediately deliver the study drug to the outpatient clinic for administration to the study participant. A final volume of ~200 ml of SGT-53 in 5% Dextrose will be infused over 90-120 minutes intravenously via a newly inserted central venous line or following flushing of an intact central venous line. Infusion must be completed as soon as possible, but no later than within eight hours of dilution of SGT-53 in dextrose.

If infusion reactions occur, acetaminophen, diphenhydramine, steroids or other medications may be given for symptom control as needed. Although prolonged use of systemic corticosteroids to prevent allergic reactions is discouraged, intermittent use of corticosteroids is permitted. Use of corticosteroids (dose, name, start/off dates) should also be documented in CRFs

9.3.1. Medications and Observations During and After Infusions of SGT-53

Four hours after completion of each infusion of SGT-53, subjects will receive acetominophen, 650 mg p.o. In addition, Demerol, 12.5 mg i.v.p.b. will be available for prn use (up to two doses) as needed for rigors. All infusions will be given where epinephrine (1:1000) 0.3-0.5 mL s.q. or i.m. (or epinephrine (1:10,000) 3-5 mL i.v.). is IMMEDIATELY available, along with dexamethasone 20 mg i.v. for prn use for suspected acute hypersensitivity reactions, including hypotension or bronchospasm. Insulin will be available for use for subjects with elevation in blood glucose levels.

Subjects will have vital sign (pulse, blood pressure and temperature) monitoring every 15 \pm 5 minutes during infusion and every 30 \pm 5 minutes for two hours after each infusion, and will be monitored closely for wheezing, change in blood pressure or signs of hypoperfusion such as cold, clammy skin, cyanosis or tachycardia. If any of these signs occur, infusion will be stopped. All patients will continue to have an i.v. fluid (at a rate

of at least 100 mL/hr) during this two hour post-infusion observation period. A 12-lead ECG will be performed weekly (2 hours post-infusion) during the first 2 weeks of cycle 1, and at the End Of Treatment (EOT) visit. If these patients receive additional rounds of SGT-53/Temozolomide a 12-lead ECG will only be performed as necessary and at the EOT visit.

9.3.2. SGT-53 Infusion Reactions

Infusion reactions are defined as any adverse event that occurs during the infusion of SGT-53 or during the two hours following completion of the infusion. Hypersensitivity reactions are those events defined by NCI criteria, e.g., bronchospasm, dyspnea, etc.

If infusion reactions occur during the infusion of SGT-53, the infusion will be discontinued and appropriate medical care administered. SGT-53 is to be administered only by physicians or nurses with training and experience with the administration of chemotherapeutic agents. All medications and interventions used to treat infusion reactions will be recorded and reviewed by the DSMB at the routine scheduled meetings (see Section 14).

The SGT-53 infusion may resume at a slower infusion rate if the symptoms resolve within two hours. If the infusion recurs at the same grade or higher, the infusion will be terminated and no further infusions of SGT-53 administered to that patient.

If a hypotensive reaction (BP < 90 systolic) occurs during infusion of SGT-53, infusion should be discontinued and not resumed during that visit. SGT-53 infusions may resume if the symptoms of hypotension have resolved by the time of the next scheduled infusion. Should this occur during SGT-53 infusions and not resolve within 24 hours the patient will not receive any further treatments (neither Temozolomide nor SGT-53) that week. The treatments will begin again the following Monday, repeating the interrupted week.

Should a second acute hypotensive reaction (BP < 90 systolic) occur during infusion of SGT-53 the patient will be removed from protocol and be replaced.

In the event that an infusion reaction consists of respiratory wheeze, including symptomatic bronchospasm or any grade 3 or 4 hypersensitivity reaction, the infusion is to be permanently discontinued and the patient replaced.

If infusion reactions occur, acetaminophen, diphenhydramine, steroids or other medications may be given for symptom control as needed. Although prolonged use of systemic corticosteroids to prevent allergic reactions is discouraged, intermittent use of corticosteroids is permitted. Use of corticosteroids (dose, name, start/off dates) should also be documented in CRFs

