For grade 2 events of increased bilirubin, AST, ALT, dyspnea, or DIC, the dose of SGT-53 can be held for up to two weeks. If the grade 2 event resolves within two weeks, then infusion of SGT-53 can resume at the same dose per calendar at incident week + 1-2 weeks (i.e., treatment would be made up and moved 1-2 weeks later).

For non-hematological events other than increased bilirubin, AST, ALT, dyspnea, or DIC, participants who develop a > or = to grade 2 toxicity (except for alopecia, or fever, chills, hypotension that respond to treatment) or grade 3 fatigue will discontinue twice-

weekly infusions until the toxicity level reduces to at least grade 1. Infusions will be held for one week intervals, and infusions that are withheld will be made-up (i.e. moved 1-2 weeks later). If the toxicity does not resolve within two weeks, study drug will be discontinued.

In the event that a patient is removed from the study for reasons other than toxicity, they can be replaced at the same dose level.

Patients who go off-treatment after receiving any infusions of SGT-53 will be considered eligible for evaluation of toxicity. Patients withdrawing consent prior to initiation of therapy will be replaced at the same dose level.

9.4.1. Patient follow up after study discontinuation:

All patients who received treatment with SGT-53 must be followed-up for 30 days after discontinuation of study drug. The 30-day follow-up visit should include a physical examination, vital signs, concomitant medications and assessment of AEs/SAEs and Urine analysis. Blood samples will be taken for: Hematology (CBC with differential, platelet count), Chemistries (BUN, Cr, Na⁺, K⁺, CO₂, Cl, Mg⁺⁺, Ca⁺⁺, phosphorus, albumin, alkaline phosphatase, ALT, AST, total bilirubin, total protein, glucose, LDH), PT/PTT, and D-dimer. Patients who permanently discontinue study drug(s) for reasons other than complete response, progression, or death should also have visits approximately every 2 months for the first year that should include a MRI, physical examination, vital signs, and recording of concomitant medications for glioblastoma.

Patients who are withdrawn from study treatment due to a complete response will have the 30-day follow-up visit as described above. Further follow-up visits every 2 months will include only a physical/neurological exam, concomitant medications, vital signs and a MRI.

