9.7.1. SGT-53 and/or Temozolomide

Table 9.7.1. reviews management of **non-hematologic** toxicities as they pertain to both study agents SGT-53 and/or Temozolomide.

Toxicity	Grade 1	Grade 2	Grade 3	Grade 4
Hyperbilirubin-	Continue both	Hold both until	Discontinue	Discontinue
emia	at same dose	grade 1 or less	TMZ, hold	TMZ, hold
Ciliu		in 2 weeks	SGT-53 until	SGT-53
		in 2 woods	grade 1 or less	until grade 1
			(up to 2	or less (up to
			weeks)*	2 weeks)*
AST &/or ALT	Continue both	Hold both until	Discontinue	Discontinue
	at same dose	grade 1 or less	TMZ, hold	TMZ, hold
		in 2 weeks	SGT-53 until	SGT-53
			grade 1 or less	until grade 1
			(up to 2	or less (up to
			weeks)*	2 weeks)*
Dyspnea not	Continue both	Hold both until	Discontinue	Discontinue
associated with	at same dose	grade 1 or less	TMZ, hold	TMZ, hold
infusion		in 2 weeks	SGT-53 until	SGT-53
			grade 1 or less	until grade 1
			(up to 2	or less (up to
			weeks)*	2 weeks)*
DIC	Continue both	Hold both until	Discontinue	Discontinue
	at same dose	grade 1 or less	TMZ, hold	TMZ, hold
		in 2 weeks	SGT-53 until	SGT-53
			grade 1 or less	until grade 1
			(up to 2	or less (up to
			weeks)*	2 weeks)*
Fatigue	Continue both	Continue both	Hold both until	Discontinue
	at same dose	at same dose	grade 1 or less	both
			in 2 weeks	
Infusion	May	May		
reaction	rechallenge	rechallenge		
	after 1 st event,	after 1 st event,	Discontinue inciting agent**	
	if resolves in 2	if resolves in 2		
	h**	h**		
Hypotension	See Section	See Section	See Section 9.3.2	•
during infusion	9.3.2.	9.3.2.		

Other non-	Continue both	Hold both until	Hold both until	Discontinue
hemetoxicity***	at same dose	grade 1 or less	grade 1 or less	both
		in 2 weeks	in 2 weeks	

^{*}If toxicity reduces to grade 1 or less in 2 weeks, patient may continue SGT-53 until end of cycle at discretion of investigator.

***Other non-heme toxicity refers to any non-heme toxicity at least possibly related to SGT-53, or temozolomide with the exception of alopecia, inadequately treated nausea, vomiting, diarrhea, or fever, chills or hypotension which respond promptly to treatment and lasts less than 24 hours.

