For grade 2 events of increased bilirubin, AST, ALT, dyspnea, or DIC, the dose of SGT-53 and Temozolomide can be held for up to two weeks. If the grade 2 event reduces at least to grade 1 within two weeks, then infusion of SGT-53 and Temozolomide can resume at the same dose per calendar at incident week + 1-2 weeks (i.e., treatment would be made up and moved 1-2 weeks later).

For non-hematological events other than increased bilirubin, AST, ALT, dyspnea, or DIC, participants who develop a > or = grade 2 toxicity (except for alopecia, fever, chills or hypotension that respond to treatment) or grade 3 fatigue will discontinue twice-weekly infusions until the toxicity level reduces to at least grade 1. Infusions will be held for one week intervals, and infusions that are withheld will be made-up (i.e. moved 1-2 weeks later). If the toxicity does not resolve within two weeks, study drug will be discontinued.

A minimum of 2-week rest period will be required if there is grade III or greater non-hematologic toxicity related to SGT-53/Temozolomide that cannot be controlled with supportive medications/measures. After the minimum 2-week rest period and the toxicity has resolved to a grade II or better, the patient will resume taking the drug at a reduced dose level as shown in Table 9.7.2b below.

Subjects who receive less than four of twelve of the intended drug infusions, due to experiencing these grade 2 events that have not resolved as described above, and that are determined by the PI to be at least probably related to SGT-53, will be considered to have experienced a DLT.

Patients forced to discontinue temozolomide due to a temozolomide-related toxicity (e.g., grade 3, 4 hypersensitivity) will be removed from the study.

^{**}Note that infusion reactions are discussed in detail in Section 9.3.2.

9.7.2. Temozolomide

Table 9.7.2a. reviews management of hematologic toxicities associated with Temozolomide treatment. Note that there are no dose adjustments for anemia.

	Grade 1	Grade 2	Grade 3 or Grade 4
Neutropenia	< LLN to	<1500 to	Grade 3: <1000 to 500/mm ³
	$1500/\text{mm}^3$	$1000/\text{mm}^3$	Grade 4: <500/mm ³
			If resolves to grade ≤ 2 within 14
	Proceed at	Proceed at	days, rechallenge at same dose of
	current dose	current dose	SGT-53, and reduce dose of TMZ
			in increments after each event
			according to Table 9.7.2b below,
			i.e. in Cycle 1reduce to 100
			mg/m ² after the first event, in
			Cycle 2 reduce to 150 mg/m2

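### After a first grade 3–4 SGT-53 infusion reaction that clears within two hours, Section 9.3.2 permits same-visit resumption where Table 9.7.1 says to discontinue; the overlap is narrow

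*Combined protocol and SAP*

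**What the plan says.** Section 9.3.2 starts from a wide definition: "Infusion reactions are defined as any adverse event that occurs during the infusion of SGT-53", or in the two hours after it ends. Neither grade nor relatedness enters. When a reaction occurs during the infusion, the infusion is stopped and the patient treated. Then: "The SGT-53 infusion may resume at a slower infusion rate if the symptoms resolve within two hours". If the reaction comes back at the same or a higher grade, that infusion ends and the patient receives no more SGT-53.

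Two kinds of reaction get their own rule in 9.3.2. Systolic pressure below 90 rules out resumption at that visit. The other rule, which is a permanent stop with replacement of the patient, begins: "In the event that an infusion reaction consists of respiratory wheeze, including symptomatic bronchospasm or any grade 3 or 4 hypersensitivity reaction".

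Table 9.7.1 has a separate row for infusion reactions. At grades 1 and 2 it allows rechallenge after a first event that resolves in two hours. At grades 3 and 4 it says "Discontinue inciting agent". (In the text as extracted the instruction appears once. I read it as spanning both grade columns.) A footnote to the row refers the reader to 9.3.2 for detail.

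**The concern.** This is a rule that staff apply at the bedside while the patient is still in the chair. A site working from 9.3.2 may restart the drug the same day after a grade 3 or 4 reaction. A site working from the table would not. The table uses the same two-hour window as 9.3.2 but adds a grade condition that 9.3.2 lacks, so one section permits what the other forbids. What is at stake is one patient's re-exposure to SGT-53 after a severe reaction, and consistent handling between two sites. The efficacy design is not at stake.

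**Working it through.** No figure in the plan bears on this, so the check is a trace of the rules, followed by a rough bound on frequency.

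**Test case.** A first grade 3 fever or chills reaction begins during the infusion, is treated, and is gone within two hours. There is no wheeze or bronchospasm, and systolic pressure stays at 90 or above.

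| Rule | Result in the test case |
|---|---|
| 9.3.2, resumption | Permitted at a slower rate, same visit |
| 9.3.2, pressure below 90 | Not triggered |
| 9.3.2, wheeze or grade 3–4 hypersensitivity | Not triggered, if treated fever or chills is not hypersensitivity |
| Table 9.7.1, infusion-reaction row | Discontinue |
| 9.7.1, one-week hold (same rule in 9.4) | Exempt: "except for alopecia, fever, chills or hypotension that respond to treatment" |
| Table 9.7.1, row for other non-hematologic toxicity | Exempt under its footnote if the response is prompt and the event lasts under 24 hours |
| 9.7.1, two-week rest | Covers "grade III or greater non-hematologic toxicity related to SGT-53/Temozolomide that cannot be controlled with supportive medications/measures"; an event gone within two hours was controlled |
| 9.4, grade 4 withdrawal reason | Needs failure to resolve within 14 days |

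The infusion-reaction row is therefore the only text that stops SGT-53 here, and 9.3.2 permits restarting it. For most other grade 3–4 reactions, the hold rules or the row for other non-hematologic toxicity also stop or delay dosing, so the clean conflict is confined to fever and chills.

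**Is fever or chills hypersensitivity?** Section 9.3.2 refers to NCI criteria and gives bronchospasm and dyspnea as examples. Section 9.2 gives pyretic reactions their own prophylaxis, and Section 14 lists fever apart from hypersensitivity. Against this, Section 4.2 uses the term for reactions that include low-grade fever and chills. On that broader use, 9.3.2 already agrees with the table.

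**Does any text rank the two?** Section 9.7.3 tells investigators to follow Table 9.7.1 when modifying SGT-53 unless patient safety calls for urgent action; it does not name 9.3.2. The row's footnote points the other way, to 9.3.2. Section 9.6 calls the parameters a guide and asks for consultation with the Medical Monitor and the Sponsor. The weight favours the table, but there is no explicit ranking.

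**How often?** Section 4.4.1 reports 11 Phase 1 monotherapy patients. The only grade 3 event listed is one case of fatigue, and the three grade 4 events were classed as unrelated or unlikely to be related. Section 11.6 describes first-infusion fever and hypotension as grade 1–2. Taking this as 0 of 11:

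- One-sided 95% exact upper limit: 1 − 0.05^(1/11) = 0.238.
- Applied to 26 patients: 26 × 0.238 = 6.2.

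This is what 11 patients cannot exclude. It is not a forecast. Doses were 0.6 to 3.6 mg without temozolomide, the detailed event table was not in the text reviewed, and the eight Phase 1b patients could not be added for the same reason.

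**Dosing that turns on the answer.** Cycles 1–3 plan 6 × 3 = 18 infusions. If discontinuing is permanent, which the table does not say, a reaction at infusion k removes 18 − k later infusions: 17 at k = 1, 12 at k = 6, none at k = 18. This measures treatment forgone by stopping, not harm from resuming.

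**The case against.** The best reply is that the texts can be read together. Section 9.3.2 is permissive, the table is grade-specific, and a site that stops complies with both. Section 9.7.3 instructs investigators to follow the table, and the only ground it gives for departing from it is patient safety, which hardly argues for re-infusing after a severe reaction. Even a site that resumes does so slowly, after symptoms have cleared, with a definitive stop if the reaction returns at the same or a higher grade, and 9.6 expects consultation. The residual case is small and depends on how fever and chills are classified.

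Nearly all of this stands, and it keeps the point minor. It does not remove the mismatch. Section 9.7.3 is a general instruction placed under de-escalation, and the people consulted under 9.6 would be reading the same two texts. The hypotension row of the table defers to 9.3.2 at every grade, while the infusion-reaction row gives its own order at grades 3–4. The table was therefore not simply leaving reactions to 9.3.2.

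A reader might go further and infer that the protocol lets sites re-infuse freely after any severe reaction, or that nothing points to the table. The documents support neither: wheeze, grade 3–4 hypersensitivity and low pressure are carved out, recurrence ends treatment, and 9.7.3 names the table.

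**Conclusion.** The conflict is real but confined to a first grade 3–4 reaction, during the infusion, that clears within two hours and is not hypersensitivity, wheeze or systolic pressure below 90. It is clearest for treated fever or chills and rests on these not being classed as hypersensitivity. Stopping is the more natural reading and satisfies both texts, but 9.3.2 as written permits the opposite.

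It is probably rare. A reader might take about 6 of 26 as the number expected to be affected; it is only an upper limit from 0 of 11, and it assumes that none of the Phase 1 grade 4 events was an infusion reaction of this kind. Sample size, the Simon decision rule and error rates are unaffected. This is a minor correction to a safety rule.

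**What to change.** Change the resumption rule in 9.3.2 in two places.

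1. Put a condition before the existing sentence so that it applies only after a first grade 1 or 2 infusion reaction, other than those handled later in the section. The rest of the sentence ("The SGT-53 infusion may resume at a slower infusion rate if the symptoms resolve within two hours") can stay.
2. Add: after a grade 3 or 4 infusion reaction, other than hypotension handled below, the infusion is not resumed at that visit. SGT-53 is discontinued as in Table 9.7.1 unless the event is judged unrelated to SGT-53. In that case dosing may restart at the next scheduled infusion once the event has resolved to grade 1 or less.

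The exception for unrelated events is needed because 9.3.2 counts any adverse event in the window, while the table acts on the inciting agent. It has to state its own restart condition. Sending such events back to the hold rules would leave treated fever and chills with no rule, since those rules exempt them. A clause that any longer hold under 9.4 or 9.7.1 still applies would keep the new text from cutting across those sections. The wording refers to the table without adding that the stop is permanent. With the grade limit in place the two texts agree, so no separate statement of precedence is needed.

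The cost is about two sentences and no new procedures. The downside is that an occasional patient with a brief, related grade 3 reaction stops SGT-53.

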Reverse transcription PCR to determine transgene expression is not applicable for these studies because it would not be able to unequivocally establish that the p53 protein detected was from the exogenous transgene. In contrast, since we have designed primers that included part of the plasmid vector backbone, only the exogenous DNA is amplified. This DNA PCR approach was used to detect the presence of the transgene in the tumors in the Phase I trial (See Figures 16 and 17 in Section 4.4.1.1) and will be used for these studies. The presence of at least 30 copies of exogenous p53 in the tumors sample will be considered positive evidence of drug penetration.

All of the patients in the trial will receive the same dosing of the combination of SGT-53 and TMZ (6 doses of SGT-53 and 5 doses of TMZ every 4 weeks for three 4 week cycles) and thus patients with or without surgical resection for tumor analysis will be used for the Simon two stage calculation. Even for the patients who undergo the optional surgical resection for tumor analysis PFS6 is the primary endpoint. No TMZ will be administered during the time these patients receive the two doses of SGT-53 prior to the resection. Exogenous p53 expression is transient. The patients who receive surgery will not begin treatment for 2-3 weeks post-surgery. Previous studies have demonstrated that there is no indication of the exogenous wtp53, even by DNA PCR, after this length of time. Thus, there will be no additional residual DNA present from the two pre-surgery doses of SGT-53 by the time the combination therapy being evaluated is initiated.

According to the Simon Minimax design, our study, with its sample size of n = 26, has a 10% probability of rejecting (a) the hypothesis of a PFS6 15% (P0) (the historical PFS6 rate) and a 70% probability of accepting (1-b) the hypothesis of a PFS-6 of 30% (P1). If two, or fewer of the first 18 patients were progression free at 6 months, PFS-6 would be considered <15% and the study terminated. Otherwise, the study would be completed, the accrual target being 26 patients. If six or fewer of the 26 patients were progression-free at 6 months, then no further investigation of the treatment regimen would be considered warranted. PFS6 and secondary endpoints progression free survival and overall survival will be evaluated using the Kaplan-Meier product-limit survival curve methodology.

4.6.5. Study Objectives:

Primary:

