9.5. Replacement policy

Patient replacement will be decided by the Safety Monitoring Committee.

9.6. **Dose Modification**

Reduction/interruption of dosing for adverse events may take place at any time. Below are guidelines for dose modification for drug-related toxicities as well as guidelines for their management. These parameters are only a guide and are not intended to supersede the clinical judgment of the treating physician. All adjustments should be made in consultation with the Medical Monitor and the Sponsor.

All dose modifications should be based on the worst preceding toxicity. If study treatment is being held due to toxicity, scheduled visits and all assessments should continue to occur except the dosing of the study drug.

9.7. **Dose Modification Plans:**

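### Repeating the interrupted week after prolonged SGT-53 hypotension (Section 9.3.2), applied literally to a Day 11 event, gives 7-8 temozolomide doses in the cycle instead of 5

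*Combined protocol and SAP*

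**What the plan says.** Section 9.3.2 covers a hypotensive reaction (systolic below 90) during an SGT-53 infusion. The infusion is stopped for that visit. If the reaction has not resolved within 24 hours, "the patient will not receive any further treatments (neither Temozolomide nor SGT-53) that week". The next sentence is the restart rule: "The treatments will begin again the following Monday, repeating the interrupted week". A second such reaction removes the patient from protocol.

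The planned amount of TMZ is consistent elsewhere. Section 4.6.4 gives "6 doses of SGT-53 and 5 doses of TMZ every 4 weeks for three 4 week cycles". Section 9.1.1 gives TMZ "daily, for 5 days in Cycle 1; 200 mg/m² daily for 5 days in Cycles 2 and 3", after 150 mg/m² in Cycle 1. Sections 5 and 9 place TMZ on Days 9-13 and SGT-53 on Days 1, 4, 8, 11, 15 and 18.

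Four other provisions bear on the restart:

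- Table 9.7.1 sends hypotension during infusion back to Section 9.3.2. Its footnote on other non-hematologic toxicity exempts only "hypotension which respond promptly to treatment and lasts less than 24 hours".
- For other non-hematologic events, Section 9.7.1 says that "infusions that are withheld will be made-up (i.e. moved 1-2 weeks later").
- The same section says: "A minimum of 2-week rest period will be required if there is grade III or greater non-hematologic toxicity" that is related to the study drugs and cannot be controlled by supportive measures.
- Section 9.6 says: "All adjustments should be made in consultation with the Medical Monitor and the Sponsor".

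**The concern.** The hold names both drugs, and the restart sentence then refers to the treatments in general, so the natural antecedent is both. Repeating a week ordinarily means giving it again. Nothing in Section 9.3.2 credits TMZ already taken or caps the cycle. A site that follows the sentence as written after a Day 11 event would give a second full five-day TMZ course about a week after the first doses, to a patient who has just had prolonged hypotension. Section 7.1 describes myelosuppression as dose-limiting for TMZ. Two sites could also dose the same situation differently.

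**Working it through.** **Inputs.** TMZ Days 9-13 and SGT-53 Days 1, 4, 8, 11, 15, 18 (Sections 5 and 9); 150 mg/m² in Cycle 1 and 200 mg/m² later as tolerated; Monday/Thursday or Tuesday/Friday infusions (Section 9.1.1); restart on the following Monday (Section 9.3.2).

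**1. The planned figure.** 13 − 9 + 1 = 5 doses. That is 5 × 150 = 750 mg/m² in Cycle 1 and 5 × 200 = 1,000 mg/m² at the higher dose. This agrees with Sections 4.6.4 and 9.1.1.

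**2. Calendar of a Day 11 event.** On Monday/Thursday with Day 1 a Monday, Day 11 is a Thursday. The restart is Monday Day 15 and the repeated TMZ falls on Days 16-20. On Tuesday/Friday the restart is Monday Day 14 and the repeated TMZ falls on Days 15-19. Both fit within 28 days.

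**3. Literal repeat.** Total = doses taken before the stop + 5.

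| TMZ taken before the stop | Total doses | Against 5 | mg/m² at 150 (plan 750) | mg/m² at 200 (plan 1,000) |
|---|---|---|---|---|
| Days 9-10 (Day 11 dose held) | 2 + 5 = 7 | +40% | 1,050 | 1,400 |
| Days 9-11 | 3 + 5 = 8 | +60% | 1,200 | 1,600 |
| Days 9-12 (Day 12 dose before the 24-hour mark) | 4 + 5 = 9 | +80% | 1,350 | 1,800 |

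**4. Other infusion days.** A Day 8 event gives 0 + 5 = 5, or 1 + 5 = 6 if the Day 9 dose precedes the 24-hour mark. Days 1 and 4 give 0 + 5 = 5. Days 15 and 18 give 5 + 0 = 5. Only one of six infusion days gives 7 or more.

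**5. Dose intensity if the cycle lengthens.** The plan does not say whether the repeated week pushes the cycle to 28 + 7 = 35 days. If it does, the comparison is with 5/28 doses per day: (7/35)/(5/28) = 1.12 and (8/35)/(5/28) = 1.28, so about +12% and +28%. The remote 9-dose case gives (9/35)/(5/28) = 1.44.

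**6. SGT-53 under the same reading.** Infusions started: Days 1, 4, 8 and 11 (4, the last one interrupted), repeated Days 8 and 11 (2), then Days 15 and 18 as originally numbered (2). 4 + 2 + 2 = 8, against 6 planned.

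**7. Whether other text settles the TMZ count.** It does not. The five-dose statements describe the uninterrupted schedule. The footnote could bring hypotension lasting beyond 24 hours under the general hold, but the make-up sentence that goes with it speaks of infusions, and TMZ is oral. The make-up sentence in Section 9.7.1 that does name TMZ is confined to grade 2 bilirubin, AST, ALT, dyspnea or DIC. If the event is also grade 3 or higher, related and uncontrolled, the two-week rest conflicts with a Monday restart.

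**8. Blood counts.** Counts are weekly (Section 10.2.3). On the Monday/Thursday calendar, the Day 15 count is 15 − 9 = 6 days after the first TMZ dose and one day before the repeated course. Section 7.1 reports median nadirs of 26 days (platelets) and 28 days (neutrophils) in refractory anaplastic astrocytoma. If those are counted from the first dose (an assumption), they fall on Days 35 and 37, well after the repeated course. Counts would mainly protect the next course.

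**The case against.** The best reply is that five doses per cycle is stated in several places, so a site giving seven or more would override all of them on one phrase in a section about infusion reactions. The sponsor probably meant missed doses only. That stands as a reading of intent, but the sentence does not say so.

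Second, Section 9.6 requires consultation on adjustments, and Table 9.7.1 brings Section 9.3.2 within reach of that rule. This is the one safeguard that acts before the extra doses, and it may well catch the problem. It is general, however, and a site following a written restart rule may not regard itself as making an adjustment.

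Third, the chain is long: a first reaction, at one particular infusion of the cycle, unresolved at 24 hours, recovered by Monday, then a literal TMZ repeat. The 9-dose case further needs TMZ given on Day 12 to a patient still hypotensive. This stands and lowers the severity.

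Fourth, percentages per cycle show the excess at its largest. A 35-day cycle gives the smaller rises in step 5. Seven doses in Cycle 1 (1,050 mg/m²) is only 5% above the 1,000 mg/m² planned for Cycle 2, although that dose is conditional on Cycle 1 tolerance.

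Stronger readings are tempting but unsupported. A reader might take the 8 of 11 Phase 1 patients with hypotension (Section 4.4.1) to mean the case will be common. Those events were grade 1-2, and Section 11.6 ties hypotension to the first infusion, in a week without TMZ. A reader might also infer harm to the efficacy result. The Simon rules in Section 4.6.4 count patients progression-free at 6 months, and nothing in the documents links this ambiguity to PFS6.

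**Conclusion.** The point holds as a low-severity dosing-safety correction. Read literally, the restart rule gives 7-8 TMZ doses after a Day 11 event instead of 5, and 9 only in a remote variant. The excess is 40-60% per cycle. If the cycle extends to 35 days, dose intensity rises by about 12-28%. These figures assume that the repeat covers all of Days 8-14 for both drugs. The documents give no frequency for the triggering event; its conditions make it rare. They do not show that the sponsor intends the extra doses or that sites would give them. Efficacy conclusions are unaffected. The 8 SGT-53 starts follow from the same wording and are a question for the sponsor, since a repeat of the infusions may be intended.

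**What to change.** Add to Section 9.3.2, directly after the restart sentence:

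> TMZ doses already taken in the interrupted week count toward the cycle; only TMZ doses not given are made up, on the corresponding days of the repeated week, and TMZ is not to exceed 5 daily doses per cycle.

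The totals are then 2 + 3, 3 + 2 or 4 + 1 = 5. On the Monday/Thursday calendar, with Days 9-10 taken, the missed Days 11-13 are given on Days 18-20. That is after the repeated Day 8 infusion (Day 15) and starting on the day of the repeated Day 11 infusion (Day 18), which respects the aim in Section 4.6.1 of having p53 expressed when TMZ is given.

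The sponsor should also confirm that 8 SGT-53 infusion starts in the cycle are intended. The added sentence does not resolve the overlap with the two-week rest in Section 9.7.1; saying which rule takes precedence would close that too.

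The cost is a one-sentence protocol edit, with no added visits, procedures or patients.
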